5.2 Treatment Assignment

5.2.1 Subject Identification Numbers

After signing the informed consent form, each subject will be assigned a unique screening number by the site staff. All screening numbers will be assigned in strict numerical sequence at a study center and no numbers will be skipped or omitted. Subjects who meet all entry criteria (ie, all the inclusion and none of the exclusion criteria) will be confirmed for enrollment. The screening numbers will be used to identify all enrolled subjects throughout the study.

5.2.2 Enrollment and Method of Assigning Subjects to Treatment Groups

This study is open-label with consecutive enrollment. When a potential subject is identified, the investigator must contact Graybug Vision's designated project manager or assigned team member managing enrollment to confirm availability for enrollment/dosing group in the study.

5.3 Study Drug Packaging, Labeling, and Storage

The study drug will be packaged, labeled, and supplied by Graybug Vision's designated supplier. GB-102 will be supplied in sterile, single use, glass vials. One single dose vial, one pre-filled syringe with hyaluronic acid and required materials for reconstitution and syringe preparation for IVT injection will be included in the kits. The designated medication kits should be stored at 2-8°C (36-46°F) and prevented from freezing. A second kit will be provided to include ancillary supplies such as needles, syringes, a drape cloth, alcohol spray, etc. to use during the reconstitution process. The ancillary supplies kits may be stored at room temperature. Additional details are provided in the pharmacy manual.

Rescue medication allowed is any anti-VEGF (aflibercept, bevacizumab, or ranibizumab). The Sponsor will not supply rescue medication nor ancillary supplies used to administer these agents. These anti-VEGF agents should be stored in accordance to the standard practices of the site.

All medication and ancillary supplies kits will be labeled with numbers. The label will also specify the storage conditions and state that the study medication is limited to investigational use.

The study drug must be stored in a secure area and administered only to subjects who entered the clinical study, at no cost to the subject, in accordance with the conditions specified on the study medication kit label and the pharmacy manual.

Only assigned individuals authorized by the investigator may have access to the study drug.

5.4 Study Drug Compliance

All notifications for assignment of medication kits are to be maintained with the study source documents. Additionally, the date, time of study treatment, and the name of the injecting investigator must be documented for each subject in the source record.

5.5 Study Drug Accountability

The investigator must keep accurate accounting of the number of medication kits received from Graybug Vision's designated vendor, the number dispensed to the subjects, and the number returned to the vendor during and at the completion of the study. A detailed dispensing record must also be completed. Only an appropriately qualified person must dispense the study medication to subjects in the study. The medication is to be used in accordance with the protocol by subjects who are under the direct supervision of an investigator.

All clinical study medications/treatments and/or supplies should be stored, inventoried, reconciled and destroyed (on site) per site destruction standard operating procedure according to applicable state and federal regulations or returned to Graybug Vision's designee for destruction.

5.6 Prior and Concomitant Therapy

All past and current use of therapies (eg, aflibercept, bevacizumab, ranibizumab, pegaptanib, and/or verteporfin) to treat CNV prior to screening will be recorded. The subject's source record should include start and stop dates or dates of administration, doses, routes, frequencies, and indications for all therapies.

All other medications (prescription, over-the-counter, and herbal) and nutritional supplements taken by the subjects from 30 days prior to screening through the completion of the study will be recorded. Changes in the dosing and/or frequency of concomitant medications must be captured with new start and stop dates indicating the previous and current doses/frequencies.

5.6.1 Rescue Treatment

Rescue treatment (any anti-VEGF agent; aflibercept, bevacizumab, or ranibizumab) for all subjects enrolled is allowed at any visit following the Day 30 study assessments in subjects who meet any of the following criteria regarding decrease in BCVA and/or increase in CST:

- Decrease in BCVA:
 - ≥ 10 ETDRS letter decrease compared with best on-study (i.e., post-treatment) BCVA ETDRS letter score
- Increase in CST (any of the following criteria):
 - ≥ 75 μm compared with the average of the last 2 visit on-study (i.e., post-treatment) CST measurements (μm), and/or,
 - ≥ 100 μm compared with the lowest on-study (i.e., post-treatment) CST measurement (μm)

Before rescue treatment is administered, the assessing investigator should confirm, if possible, with the medical monitor.

Use of rescue treatment will be recorded on the case report forms (CRFs) and source documents.

5.6.2 Other Permitted Medications

Medications that are permitted during the study include the following:

- Direct thrombin inhibitor class of drugs such as warfarin, dabigatran, or rivaroxaban
- Aspirin (acetylsalicylic acid)
- Any intravitreally administered anti-VEGF therapy in the **nonstudy eye** for the treatment of wet AMD, DME, and/or RVO (aflibercept, bevacizumab, or ranibizumab)
- Any exposure to a prior investigational drug product that is fully washed out (at least 5 half-lives) and/or does not meet any of the exclusion criteria

5.6.3 Prohibited Medications

Medications that are not permitted during the study include the following:

- Use of more than 2 topical hypotensive medications for the treatment of glaucoma in the **study eye**
- Intravitreal steroid injection (eg, triamcinolone suspension)
- Any steroid implant in the study eye (eg, Iluvien[®] or Ozurdex[®])
- Oral sunitinib malate
- Any intravitreally administered anti-VEGF therapy in the **study eye** for the treatment of wet AMD, DME, and/or RVO (aflibercept, bevacizumab, or ranibizumab) unless the subject qualifies for rescue treatment per the rescue treatment criteria

5.7 Other Study Supplies

Graybug Vision or its designee will make provisions (directly or indirectly) to supply the study centers with supplies for study drug preparation (syringes, needles, vortex mixers, vial adapters, drape towels, alcohol spray, alcohol prep pads and vial stand), and blood sampling and shipment kits for sunitinib exposure assessment.

Study centers will be allowed to use their own ETDRS supplies, once verified through the BCVA certification process. Study centers will use their own medications/supplies (anti-infective ophthalmic solution, local anesthetic eye drop, dilating eye drop, povidone iodine, cotton tip swabs, sterile fields, and cellulose sponges) to prep the eye for ocular assessments and/or study drug administrations. CLIA-approved urine pregnancy test kits and lab kits for collection of Hemoglobin A1c assessment should be supplied by the site's local laboratory.

6 STUDY PROCEDURES

The study procedures to be conducted for each subject enrolled in the study are presented in tabular form in [Table 3-1](#). The procedures to be conducted are summarized by visit within [Section 6.2](#). The investigator must document any deviation from the prespecified protocol procedures and notify the Sponsor or contract research organization if/when deviations occur.

The protocol-specified procedures for a given study visit may be split across 2 days within the visit-specific window (if applicable); however, for each visit, all BCVA, ophthalmic examinations, and ophthalmic imaging must be performed on the same day and cannot be split across 2 or more days.

6.1 Subject Entry Procedures

Prospective subjects who meet the entry criteria (inclusion/exclusion criteria) defined in [Sections 4.3](#) and [4.4](#) will be considered for inclusion in this study.

The study will be discussed with each subject and a subject wishing to participate must give informed consent prior to the study center performing any study related procedures or changes in concomitant treatment. All subjects must also give authorization and other written documentation in accordance with relevant country and local privacy requirements (where applicable) prior to the study center performing any study related procedures or changes in concomitant treatment.

Each subject who provides informed consent will be assigned a screening number that will be used on all source documentation throughout the study. A subject is considered to be enrolled into the study at the time of administration of the first dose on Day 1.

Subject eligibility based on lesion characteristics must be determined by the investigator prior to subject treatment; there is no third-party confirmation of images obtained at screening or during the conduct of the study. In addition, screening laboratory test (i.e., hemoglobin A1c) must be performed, and the results must be evaluated and determined to be acceptable to the investigator prior to subject enrollment into the study.

A urine pregnancy test administered to women of childbearing potential at the Screening and Baseline visit must be negative for the subject to receive study drug at the Baseline visit.

6.2 Study Visit Procedures

6.2.1 Screening (Day -30 through Day -3)

The Screening Visit should occur 3 to 30 days before study Baseline (Day 1) to ensure that laboratory results are obtained and the investigator has confirmed eligibility. The following procedures are to be performed at this visit:

- Obtain informed consent and authorization
- Collect demographic information and medical and ophthalmic history
- Collect information about concomitant medications and procedures
- Conduct a physical examination
- Draw blood samples for hemoglobin A1c
- Conduct a urine pregnancy test on women of childbearing potential (note that additional pregnancy tests may be performed at any time/day during the study)
- Obtain vital signs (blood pressure, heart rate, height [without shoes] and weight)
- Assess BCVA (using the ETDRS protocol with manifest refraction) in both eyes
- Perform the slit-lamp biomicroscopy of both eyes
- Measure IOP (via Goldmann applanation tonometry or Tono-Pen) in both eyes (the same measurement method should be used throughout the study)
- Perform dilated ophthalmoscopy of both eyes
- Obtain SD-OCT imaging of both eyes
- Assess the subject regarding the inclusion/exclusion criteria
- Query for AEs
- If the subject meets the entry criteria, schedule the subject to return for the Baseline visit, otherwise, exit the subject from the study as a screen failure

6.2.2 Baseline (Day 1)

The following procedures are to be performed:

- Review concomitant medications and procedures
- Query for AEs
- Conduct a urine pregnancy test on women of childbearing potential (note that additional pregnancy tests may be performed at any time/day during the study)
- Obtain vital signs (blood pressure and heart rate)

- Assess BCVA (using the ETDRS protocol with manifest refraction) in both eyes
- Perform the slit-lamp biomicroscopy of both eyes
- Measure IOP (via Goldmann applanation tonometry or Tono-Pen) in both eyes (must be performed prior to the IVT injection of study drug)
- Perform dilated ophthalmoscopy of both eyes
- Obtain SD-OCT imaging of both eyes

After completion of these procedures, if the subject still meets entry criteria, and the investigator has confirmed subject eligibility based on ocular inclusion/exclusion criteria, the results from the screening blood chemistry (i.e., hemoglobin A1c) and urine pregnancy tests, as well as BCVA assessments, and obtained sponsor confirmation to enroll, the subject can be prepared for treatment.

- When medically appropriate, dispense pre-injection and postinjection anti-infectives according to standard clinic procedure at the study center
- Perform the IVT injection of the allocated dose of study drug into the study eye
- Perform the postinjection assessment of the study eye checking for count fingers or hand motion vision within 15 minutes after injection while ensuring that the subject has minimal to no movement of the head and avoids significant eye movement during the 15 minutes after injection. If needed, the subject can be examined (eg, additional IOP or ophthalmoscopy) per the discretion of the injecting investigator prior to going home.
- Perform CFP in the study eye to document the position of the depot and the status of the visual axis
- Schedule the subject to return for the Week 2 visit
- All subjects will receive a telephone call from qualified study center personnel as a safety follow-up the day after the IVT injection procedure

6.2.3 Week 2 and Months 1, 2, 3, 4, and 5

The visits windows are as follows: Week 2 (Day 14 \pm 2) and Months 1, 2, 3, 4, and 5 (Day 30 \pm 4, Day 60 \pm 7, Day 90 \pm 7, Day 120 \pm 7, Day 150 \pm 7).

The following procedures are to be performed at each of the visits unless otherwise specified:

- Review concomitant medications and procedures
- Query for AEs

- Conduct a urine pregnancy test on women of childbearing potential at Month 3 only (note that additional pregnancy tests may be performed at any time/day during the study)
- Assess BCVA (using the ETDRS protocol with manifest refraction) in both eyes
- Perform the slit-lamp biomicroscopy of both eyes
- Measure IOP (via Goldmann applanation tonometry or Tono-Pen) in both eyes
- Perform dilated ophthalmoscopy of both eyes
- Obtain SD-OCT imaging of both eyes
- Perform CFP in the study eye to document the position of the depot and the status of the visual axis
- Schedule the subject to return for the next study visit

6.2.4 Month 6 (Day 180 ± 7) / Early Termination

The following procedures are to be performed:

- Review concomitant medications and procedures
- Query for AEs
- Conduct a physical examination
- Conduct a urine pregnancy test on women of childbearing potential
- Obtain vital signs (blood pressure, heart rate and weight)
- Assess BCVA (using the ETDRS protocol with manifest refraction) in both eyes
- Perform the slit-lamp biomicroscopy of both eyes
- Measure IOP (via Goldmann applanation tonometry or Tono-Pen) in both eyes
- Perform dilated ophthalmoscopy of both eyes
- Obtain SD-OCT imaging of both eyes
- Perform CFP in the study eye to document the position of the depot and the status of the visual axis
- Exit the subject from the study

If follow-up is needed after the early termination visit, it should occur as a poststudy, unscheduled visit at the discretion of the investigator.

Subjects with an ongoing SAE at this visit should be followed until the event resolves or stabilizes as described in [Section 8.8](#).

6.3 Screen Failures

Subjects who miss a scheduled visit prior to the baseline (Day 1) visit or do not qualify for enrollment in the study will be considered screen failures.

6.4 Unscheduled Study Visits

Unscheduled visits may be necessary due to AEs or other reasons. The investigator may examine a subject as often as is medically necessary while the subject is enrolled in the study. Any follow-up that is performed to monitor subject safety should be recorded as an unscheduled visit. The following procedures may also be conducted at an unscheduled visit as well as any procedures deemed necessary by the investigator to assess safety:

- Monitor and query AEs
- Record changes in concomitant medications

6.5 Subject Discontinuation

Subjects should not be withdrawn due to an AE (unless related to subject death), pregnancy, lack of efficacy, protocol deviations, or other reason except for the subject withdrawing consent, or being lost to follow-up. If a subject is enrolled in the study and discontinues from treatment, he/she should be encouraged to remain in the study through study completion to allow continued safety assessment and monitoring, unless the subject withdraws consent.

In the event of subject withdrawal prior to the end of the study, study assessments for the early termination visit should be conducted whenever possible. If a subject withdraws from the study, he or she may not re-enter the study. At the time of withdrawal, the investigator should advise the subject of other available treatment options. When a subject withdraws from the study, the reason(s) for withdrawal will be recorded on the CRF.

In the event of a subject death during the study, the date of death (as listed on the death certificate) will be used as the date of study withdrawal.

If a subject fails to return for a scheduled visit, it is the responsibility of the investigator or designee to document all efforts made to contact the subject and to determine the reason the subject did not return. If a subject cannot be contacted with 3 documented telephone call attempts, followed by a certified letter, and does not have a known reason for discontinuation (eg, withdrawal of consent), the reason for discontinuation will be recorded as “lost to

follow-up.” The date that the certified letter was mailed will be considered the date of study withdrawal.

6.6 Subject Replacement

One rescreening of a nontreated screen failure subject may be allowed.

If an enrolled (i.e., treated) subject withdraws prior to Month 3, for any reason, the subject may be replaced following discussion with the medical monitor.

6.7 Study Termination Criteria

The Sponsor may terminate this study at any time for any reason. The Sponsor also may discontinue participation by an individual investigator or study center for poor enrollment or noncompliance. At the time of study termination, any active subjects should complete the early termination visit. All ongoing AEs should be followed as appropriate and all ongoing SAEs should be followed until the resolution or stabilization.

7 STUDY ASSESSMENTS

This section describes the study assessment procedures. Refer to [Appendix 18.1](#) and [Table 3-1](#) for information regarding the timing of each assessment.

7.1 Demographic Data

Demographic data will be recorded including date of birth, sex, eye color, race, and ethnicity.

7.2 Medical and Medication History/ Concomitant Medications

Medical history will be recorded and should elicit all major illnesses, diagnoses, and surgeries for the subject within the past two years prior to screening. All ocular history will also be recorded and should be specific to eye involvement, as appropriate.

All past and current use of therapies (eg, aflibercept, bevacizumab, and ranibizumab) to treat DME/RVO prior to screening will be recorded. The subject's source record and CRF should include start and stop dates, dose, route, frequency, and indication.

Other prior and concomitant medications taken from 30 days prior to screening through the last study visit will be recorded and will include any prescription and over-the-counter medications, as well as herbal or nutritional supplements; the subject's source record should include start and stop dates, dose, route, frequency, and indication.

Prior SD-OCT assessments and visual acuity values must also be recorded for the past 24 months if available.

7.3 Physical Examination

The physical examination will consist of, at a minimum, a routine evaluation of the organ systems including general appearance, neck, head, ears, nose, throat, cardiovascular, respiratory, abdomen, and skin/extremities. At the final study visit, the physical examination will include a query of the subject to determine if changes in his/her physical condition have occurred since the screening examination.

7.4 Pregnancy Testing

Urine pregnancy testing will be conducted on women of childbearing potential as appropriate. Women of childbearing potential (ie, not postmenopausal for at least 12 months or not surgically sterile [bilateral tubal ligation, hysterectomy, or bilateral oophorectomy]) must have a negative urine pregnancy test at Screening and Baseline, and must use adequate birth control throughout the study if she has a nonsurgically sterile male sexual partner. Adequate methods of birth control include hormonal contraceptives, intrauterine contraceptive device, condom with spermicide, diaphragm with spermicide, and cervical cap with spermicide.

7.5 Blood Chemistry

Blood samples for Hemoglobin A1c will be collected using the site's local laboratory. Samples and results should be obtained prior to administration of study drug. The minimum tests to be performed include the following:

- Nonfasting chemistry (blood): Hemoglobin A1c

7.6 Vital Signs

Vitals signs will consist of blood pressure and heart rate measurements. Systolic and diastolic pressure and heart rate (bpm) will be measured after subjects have been at rest (seated) for at least 5 minutes. The same arm and method of obtaining blood pressure and heart rate should be used throughout the study. Measurements may be repeated once at the discretion of the investigator. Along with the vital signs, height (without shoes) will be measured at Screening and body weight will be measured at Screening and Month 6.

7.7 Best Corrected Visual Acuity

Manifest refraction will be conducted prior to BCVA. The BCVA assessment will be conducted for each eye, prior to dilating pupils, using the standard ETDRS protocol with back-illuminated eye charts. A study-specific manifest refraction and BCVA testing protocol is described in a separately provided BCVA Manual.

Visual acuity testing will be performed by a certified visual acuity examiner and should occur before any examination requiring contact with the eye. The same BCVA examiner should be utilized for each subject throughout the study when possible.

7.8 Slit-lamp Biomicroscopy

Slit-lamp biomicroscopy will be performed for each eye by a qualified assessing investigator at each study visit. Slit-lamp biomicroscopy, including magnification, will be performed without dilation of the pupil and consistent with standard practice. The subject will be seated during the examination. This procedure should be conducted in the same manner for all subjects and will include an assessment of each of the following as normal or abnormal:

- Eyelids
- Conjunctiva
- Cornea
- Anterior chamber
- Iris

- Pupil
- Lens

If any findings are abnormal, exact findings should be specified and noted as either clinically or not clinically significant.

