1.5.1.3 Toxicology

Sunitinib malate was originally developed as an orally administered agent for the treatment of advanced malignancies at a daily dose of 37 to 50 mg (SUTENT® capsules). The steady state plasma levels of sunitinib at the oral recommended daily dose is approximately 60 to 100 ng/mL. Based on allometric scaling from nonclinical ocular PK studies (rabbits, rats) to humans, it is estimated that a single orally administered approved dose of 50 mg sunitinib in man results in uveal tissue concentration of drug that are 1-log to 2-log orders higher than a single IVT injection of GB-102 containing 1 mg sunitinib (Peterson 2016, Speed 2012).

Three GLP ocular toxicology studies were conducted with GB-102: a single dose study in rabbits, a repeat dose study in rabbits, and a repeat dose study in minipigs.

The ocular toxicity following a single IVT injection (50 µL) of GB-102 at doses of 0, 0.25, 0.5, 1.0, and 2.0 mg/eye in pigmented rabbits was evaluated in a GLP study with up to 19 weeks observation. Assessments were conducted with *in vivo* ophthalmic examination, including ERGs, and postmortem histopathology of the enucleated eyes. The main findings included 1) time- and dose-dependent lens opacities, which were due to the high injection volume (50 µL), and 2) mild anterior and vitreous inflammation, which was due to endotoxin contamination of the test materials.

In the repeat-dose rabbit study, animals received IVT injections of 0.125, 0.25 and 0.5 mg/eye GB-102 (in volumes up to 12 µL). Animals were injected on Day 1 and Day 141 over the course of 40 weeks. GB-102 was well tolerated compared to the GLP single dose ocular toxicology study in rabbits. The main findings in the repeat dose rabbit study included transient ocular inflammation at all dose levels regardless of dose volume, which was not test article related. Focal, peripheral and inferior lens opacities occurred in 3 out of 4 groups, which were test article related.

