7.10 Dilated Ophthalmoscopy

Dilated fundus examination of both eyes will be performed in all subjects by designated qualified study center personnel (i.e., an ophthalmologist). The following will be observed for the presence of abnormalities:

- Vitreous body
- Macula
- Peripheral retina
- Choroid
- Optic nerve

If any findings are abnormal, exact description of the findings should be specified and noted as either clinically or not clinically significant. All abnormal findings that are clinically significant and were not present at baseline, will be described and reported as AEs.

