18.5 Age-Related Eye Disease Study Lens Scale

Presence and severity of nuclear sclerosis, cortical opacities, and posterior subcapsular opacities will be evaluated according to the Age-Related Eye Disease Study (AREDS) Clinical Lens Grading Protocol ([Chew 2010](#)). Biomicroscopic findings will be compared with standard photographs. The Sponsor or its delegate will supply the investigational centers with a copy of the standard photographs.

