### 13.3 Slit-Lamp Biomicroscopy Examination

A slit-lamp biomicroscopy examination of the eyelid, cornea, conjunctiva, anterior chamber, iris, pupil, lens, lens status, and Age-Related Eye Disease Study (AREDS) scores for Nuclear, Cortical, and PCS opacity will be performed at each visit. The results will be graded as normal, abnormal not clinically significant (NCS), or abnormal clinically significant (CS) for all but the lens status and AREDS scores. Lens status will be denoted phakic, pseudophakic, or aphakic. AREDS opacity scores are <1, 1, 1.5, 2, 2.5, 3, or >3. Anterior chamber cells and flare will also be assessed using categorical responses that range from 0 to 4+, as described below.

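### No specified assessment records the lens through a dilated pupil, so the trial may under-record peripheral lens opacities like those in the repeat-dose rabbit study

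*Protocol*

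**What the plan says.** Protocol 7.8 sets one pupil condition for the whole slit-lamp examination: "Slit-lamp biomicroscopy, including magnification, will be performed without dilation of the pupil and consistent with standard practice". The lens is one of the seven structures listed there, and the section asks for the same procedure in every subject.

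Appendix 18.5 covers lens grading: "Presence and severity of nuclear sclerosis, cortical opacities, and posterior subcapsular opacities will be evaluated" under the cited AREDS clinical lens grading protocol, and "Biomicroscopic findings will be compared with standard photographs". SAP 13.3 puts the grades inside the slit-lamp examination, where AREDS "scores for Nuclear, Cortical, and PCS opacity will be performed at each visit". Neither place states a pupil condition for the grading.

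Protocol 7.10 describes the other eye examination: "Dilated fundus examination of both eyes will be performed in all subjects by designated qualified study center personnel". Its list is vitreous body, macula, peripheral retina, choroid and optic nerve. SAP 13.4 has the same five structures. Table 3-1 schedules both examinations, in both eyes, at every visit from screening to Month 6.

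On toxicology, Protocol 1.5.1.3 says of the repeat-dose rabbit study: "Focal, peripheral and inferior lens opacities occurred in 3 out of 4 groups, which were test article related". Of the single-dose rabbit study it reports "time- and dose-dependent lens opacities, which were due to the high injection volume". The repeat-dose minipig study had no microscopic findings related to the test article. Protocol 5.1.1 places the depot in the inferior part of the posterior segment, off the visual axis.

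**The concern.** Safety is the primary objective. In the toxicology summary, lens opacity is the only ocular finding expressly called test article related, and it is described as peripheral and inferior. The depot also sits inferiorly in patients. With an undilated pupil the iris covers the peripheral lens; this is ordinary anatomy, not something the documents state.

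Tables 14.3.9.1 and 14.3.9.3 (slit-lamp findings and shifts in AREDS score) would be filled from that undilated examination. If they showed no lens change, a reader would take this as evidence of lens safety, when part of it could come from the viewing condition. There would also be no dilated baseline record of the lens. An opacity noticed by chance at a later dilated examination could then not be classed reliably as new or pre-existing.

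**Working it through.** **Step 1. Which assessment records the lens, and with what pupil?**

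| Assessment | Pupil | Lens listed? | Source |
|---|---|---|---|
| Slit-lamp biomicroscopy | Undilated | Yes | Protocol 7.8 |
| AREDS grades | Not stated; placed in the slit-lamp examination | Yes | Appendix 18.5, SAP 13.3 |
| Dilated ophthalmoscopy | Dilated | No | Protocol 7.10, SAP 13.4 |
| Inflammation, hemorrhage and haze scales | Slit lamp and indirect ophthalmoscopy | No | Appendix 18.4 |
| Fundus photography | Follows the dilated examination | No; depot and visual axis | Protocol 7.12, Table 3-1 |

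No row combines a stated dilated pupil with a lens record. The AREDS row inherits the undilated condition from Protocol 7.8 unless the cited grading protocol overrides it. That protocol is not among the documents.

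**Step 2. The plan's own detection figure.** Protocol 9.4 says that about 20 subjects allow detection of adverse event rates above 15% overall and above 30% per dose, with about 95% confidence. The rule of three reproduces this: 3/20 = 15% and 3/10 = 30%. As a check, the chance of at least one case is 1 − (1 − p)^n:
- n = 20, p = 0.15: 1 − 0.85^20 = 96.1%
- n = 10, p = 0.30: 1 − 0.70^10 = 97.2%

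Both figures assume that every affected subject is identified.

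**Step 3. If only a share s of affected eyes is identified.** The chance of at least one recorded case becomes 1 − (1 − s·p)^n, and the rule-of-three threshold becomes 3/(n·s). The documents give no value for s, so the range below is an assumption.

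| s (assumed) | n = 20, p = 15% | n = 10, p = 30% | Threshold overall / per dose |
|---|---|---|---|
| 1 | 96.1% | 97.2% | 15% / 30% |
| 0.9 | 94.5% | 95.7% | 16.7% / 33.3% |
| 0.75 | 90.8% | 92.2% | 20% / 40% |
| 0.5 | 79.0% | 80.3% | 30% / 60% |

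For example, at s = 0.5: 1 − (1 − 0.075)^20 = 79.0% and 1 − (1 − 0.15)^10 = 80.3%.

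**Step 4. The number at risk.** Only a natural lens can develop these opacities. Exclusion 10f bars cataract surgery only within the 3 months before screening, and SAP 13.3 records pseudophakic status, so pseudophakic study eyes can enrol. For a lens finding, n in the formulas is the number of phakic study eyes. The documents do not give it, and it may be below 20 and 10.

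**The case against.** The strongest objection concerns the AREDS grading. Appendix 18.5 is the specific instruction for it, was added by amendment, and refers to a published grading protocol that may set its own pupil condition. If that protocol requires dilation, the defect is a conflict between 7.8 and Appendix 18.5 and not a gap in what is examined. This stands as a limit on confidence. It does not remove the point: 7.8 would still tell sites the opposite, and the lens item in the 7.8 list would still be undilated.

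Second, the animal signal is narrow. The test-article attribution comes from one rabbit study with two injections (Day 1 and Day 141), whereas this trial gives one. The single-dose rabbit opacities were attributed to injection volume. Minipigs had no microscopic findings related to the test article. A single-injection study in neovascular AMD has been completed, and its results are in the Investigator's Brochure, which is not available here. All of this stands and limits how likely the event is in patients. It does not make the assessment better at recording the event.

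Third, an ophthalmologist looks through the dilated pupil of both eyes at every visit, any clinically significant ophthalmic change is an adverse event under Protocol 8.1, and BCVA is measured throughout. These routes are real. They are also incidental: no lens field is specified at the dilated examination, and a peripheral opacity off the visual axis is the kind least likely to affect acuity or prompt a complaint.

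Fourth, dilation does not expose the whole lens periphery either. The change would improve the view but would not guarantee detection.

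**Conclusion.** The point holds in a limited form, with moderate confidence. As the two documents are written, no specified assessment records the lens through a dilated pupil, and the trial may therefore under-record peripheral opacities in phakic eyes. The loss cannot be sized from the documents. The Step 3 table shows only how the plan's detection figures would respond to an assumed sensitivity. It is not an estimate of the sensitivity of the undilated examination.

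Two stronger readings are tempting and are not supported. A reader might infer that the lens goes unexamined, or that the trial will miss these opacities. The lens is examined undilated at every visit, and incidental dilated viewing and adverse event reporting remain open. A reader might also infer that, because the single-dose rabbit opacities arose at 50 µL, the volume used in this trial, they show a drug effect to be expected in patients. The protocol attributes them to the injection volume. Only the repeat-dose rabbit opacities are attributed to the test article.

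**What to change.** - **Protocol 7.8:** keep eyelids, conjunctiva, cornea, anterior chamber (including cells and flare), iris and pupil undilated. State that the lens and the Appendix 18.5 AREDS grades are assessed at the slit lamp after the dilation already done at baseline and every follow-up visit, and that the location of any opacity is recorded. The baseline grade should be taken before the injection, to fit the definition of baseline in SAP 8.3.
- **Protocol 7.10, Appendix 18.5, SAP 13.3 and 13.4:** align them with this, so that the post-dilation lens assessment appears in each. Check the cited AREDS grading protocol for a pupil condition and reconcile 7.8 with it.
- **Tables 14.3.9.1 and 14.3.9.3:** report lens results with phakic eyes as the denominator, for study and non-study eyes.

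The cost is wording in two documents, a field for opacity location, and a brief return to the slit lamp after dilation. Both eyes are already dilated for ophthalmoscopy at every visit, and adequate dilation in both eyes is an entry criterion, so no visit or procedure is added. BCVA and IOP keep their place before dilation.
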